16.2. Appendix 2. Performance Status Scales

ECOG or Zubrod		Karnofsky		Lansky	
Score	Activity	Score	Activity	Score	Activity
0	Fully active, able to carry on all pre-disease performance without restriction.	100 90	Normal, no complaints, no evidence of disease. Able to carry on normal activity; minor signs or symptoms of disease.	100 90	Fully active, normal. Minor restrictions in physically strenuous activity.
1	Restricted in physically strenuous activity but ambulatory and able to carry out work of a light or sedentary nature, e.g., light housework, office work.	80 70	Normal activity with effort; some signs or symptoms of disease. Cares for self, unable to carry on normal activity or do active work.	80 70	Active, but tires more quickly. Both greater restriction of and less time spent in play activity.
2	Ambulatory and capable of all selfcare but unable to carry out any work activities. Up and about more than 50% of waking hours.	60 50	Requires occasional assistance, but is able to care for most of his/her needs. Requires considerable assistance and frequent medical care.	60 50	Up and around, but minimal active play; keeps busy with quieter activities. Gets dressed, but lies around much of the day; no active play; able to participate in all quiet play and activities.
3	Capable of only limited selfcare, confined to bed or chair more than 50% of waking hours.	40 30	Disabled, requires special care and assistance. Severely disabled, hospitalization indicated. Death not imminent.	40 30	Mostly in bed; participates in quiet activities. In bed; needs assistance even for quiet play.
4	Completely disabled. Cannot carry on any selfcare. Totally confined to bed or chair.	20 10	Very sick, hospitalization indicated. Death not imminent. Moribund, fatal processes progressing rapidly.	20 10	Often sleeping; play entirely limited to very passive activities. No play; does not get out of bed.

16.3. Appendix 3. Response Assessment in Neuro-Oncology Brain Metastases (RANO-BM)

16.3.1. Definitions Associated with RANO-BM[46]

1. **Measurable disease** is defined as a contrast-enhancing lesion that can be accurately measured in at least one dimension, with a minimum size of 10 mm, and is visible on two or more axial slices that are preferably 5 mm or less apart with 0 mm skip (and ideally \leq 1.5 mm apart with 0 mm skip).
 - a. Additionally, although the longest diameter in the plane of measurement is to be recorded, the diameter perpendicular to the longest diameter in the plane of measurement should be at least 5 mm for the lesion to be considered measurable.
 - b. If the MRI is performed with thicker slices, the size of the measurable lesion at baseline should be at least double the slice thickness. Interslice gaps, if present, should also be considered in the determination of the minimum size of measurable lesions at baseline.
2. **Non-measurable disease**
Non-measurable disease includes all other lesions, including lesions with longest dimension less than 10 mm, lesions with borders that cannot be reproducibly measured, dural metastases, bony skull metastases, cystic-only lesions, and leptomeningeal disease.
3. **Special considerations regarding lesion measurability**
 - a. For investigators who choose to lower the minimum size limit of measurable disease to 5 mm, the RANO-BM working group strongly recommends MRI imaging with 1.5 mm slice thickness or less.

Complete response and unequivocal progressive disease can probably be interpreted even with lesions as small as 5 mm. However, measurement of small changes, such as the minimum 20% increase in the longest diameter to determine progressive disease or the minimum 30% decrease in longest diameter to determine partial response, might not be robust or reproducible. With the intrinsic uncertainty of measurements of small lesions, any lesion less than 10 mm in longest diameter should be regarded as unchanged from baseline unless there is a minimum 3 mm change in the measured longest diameter.

For studies in which CNS objective response is the primary endpoint, the RANO-BM working group generally recommends a cutoff of 10 mm to limit the study to measurable disease.

- b. **Cystic or surgical cavities** should be considered non-measurable as noted above unless there is a nodular component that measures 10 mm or more in longest diameter and 5 mm or more in the perpendicular plane. The non-nodular component (i.e., the cyst or surgical cavity) should not be included in the measurement for determination of a response.
- c. The decision to include patients with multiple lesions with a sum diameter of 10 mm or more but of which the largest lesion measures less than 10 mm should be taken with caution if objective response is the primary endpoint. If such patients are included, response should be assessed using the sum of the longest diameters of the lesions, and the response criteria should be clearly delineated in the protocol. Thin-section MRI imaging with 1.5 mm or thinner slice thickness would be necessary in this setting.

4. Methods of measurement

The same method of assessment and the same technique should be used to characterize each identified and reported lesion at baseline and during follow-up. Consistent use of imaging techniques across all imaging time points is important to ensure that the assessment of interval appearance, disappearance of lesions, or change in size is not affected by scan parameters such as slice thickness. Use of thin section imaging is particularly important for the assessment of lesions less than 10 mm in longest diameter or small changes in lesion size, or both.

Gadolinium-enhanced MRI is the most sensitive and reproducible method available to measure CNS lesions selected for response assessment. MRI is strongly encouraged as the default standard imaging technique, although CT with and without contrast could be considered in specific circumstances (e.g., countries with limited medical resources or contraindication for MRI).

5. Tumor response assessment

Only patients with measurable CNS disease at baseline should be included in protocols where objective CNS tumor response is the primary endpoint. For studies in which objective response is not the primary endpoint, the protocol must specify prospectively whether entry is restricted to those with measurable disease or if patients with non-measurable disease are also eligible.

- a. Assignment of CNS response is independent of systemic disease response. CNS lesions are to be assessed according to RANO-BM criteria, whereas non-CNS lesions would most typically be assessed according to RECIST 1.1 criteria.
- b. Generally, CNS lesions should initially be re-assessed by MRI at protocol-specified intervals 6–12 weeks apart, although there might be specific circumstances in which longer (or shorter) intervals are desirable. For patients who remain stable for extended periods of time, a longer interval between scans might be appropriate. All baseline assessments should be done as close as possible to the treatment start and no more than 4 weeks before the beginning of treatment.
- c. For previously treated lesions, we recommend documentation of how each lesion was previously treated (e.g., stereotactic radiosurgery, whole brain radiotherapy, surgical resection).
- d. When more than one measurable lesion in the CNS is present at baseline, all lesions up to a maximum of five CNS lesions should be identified as target lesions and will be recorded and measured at baseline. All measurements should be recorded in metric notation. Target lesions should be selected on the basis of their size (longest diameter) and as those that can be measured reproducibly. For patients with recurrent disease who have multiple lesions, of which only one or two are increasing in size, the enlarging lesions should be prioritized as target lesions for the response assessment.
- e. Lesions with prior local treatment (i.e., stereotactic radiosurgery or surgical resection) can be considered measurable if progression has occurred since the time of local treatment. However, careful consideration should be given to lesions previously treated with stereotactic radiosurgery, in view of the possibility of treatment effect, which is discussed below. Whether such lesions can be considered measurable should be

specified prospectively in the clinical protocol. If lesions not previously treated with local therapies are present, these are preferred for selection as target lesions.

f. A sum of the diameters for all target lesions will be calculated and reported as the baseline sum of longest diameters. All other CNS lesions should be identified as non-target lesions and should also be recorded at baseline. Measurements are not required and these lesions should be classified as present, absent, or unequivocal progression, and followed up.

16.3.2. Response assessment of target and non-target lesions[46]

Please see Table 16-3 and Table 16-4 for a partial summary of this section.

1. While on study, all CNS target lesions should have their actual measurement recorded, even if very small (e.g., 2 mm). If the lesion disappears, the value should be recorded as 0 mm. However, if the lesion is sufficiently small (but still present) to be assigned an exact measurement, a default value of 5 mm should be recorded on the case report form.
2. Lesions might coalesce during treatment. As lesions coalesce, a plane between them may be maintained that would aid in obtaining maximum longest diameter of each individual lesion. If the lesions have truly coalesced such that they are no longer separable, the vector of the longest diameter in this instance should be the maximum longest diameter for the coalesced lesion.
3. New lesions can appear during treatment. The finding of a new CNS lesion should be unequivocal and not due to technical or slice variation. A new lesion is one that was not present on prior scans.
 - a. If the MRI is obtained with slice thickness of 1.5 mm or less, the new lesion should also be visible in axial, coronal, and sagittal reconstructions of 1.5 mm or thinner projections.
 - b. If a new lesion is equivocal, for example because of its small size (i.e., ≤ 5 mm), continued therapy can be considered, and a follow-up assessment will clarify if it really is new disease. If repeated scans confirm a new lesion, progression should be declared using the date of the initial scan showing the new lesion.
 - c. In the case of immunotherapy, however, new lesions alone cannot constitute progressive disease (see below).
4. Unequivocal progression of non-target lesions can merit discontinuation of therapy.
 - a. When a patient also has measurable disease, to be deemed as having unequivocal progression on the basis of non-target disease alone there must also be an overall substantial worsening in non-target disease such that, even in the presence of stable disease or partial response in target disease, the overall tumor burden has increased sufficiently to merit discontinuation of therapy.
 - b. When the patient has only non-measurable disease, there must be an overall level of substantial worsening to merit discontinuation of therapy.
5. The RANO-BM group acknowledges the case of patients who have been treated with stereotactic radiosurgery or immunotherapy-based approaches, for whom there has been radiographical evidence of enlargement of target and non-target lesions, which do not necessarily represent tumor progression. If radiographical evidence of progression exists, but clinical evidence indicates that the radiological changes are due to treatment effect (and not to progression of cancer), additional evidence is needed to distinguish between true progression and treatment effect, in which case standard MRI alone is insufficient. The methods used to distinguish between true progression and treatment effect should be

specified prospectively in the clinical protocol. Patients can be continued on protocol therapy pending further investigation with one or more of the following options.

The scan can be repeated at the next protocol-scheduled assessment or sooner, and generally within about 6 weeks. An investigator can choose a shorter time interval if progressive symptoms or other clinical concerns arise. Continued tumor growth might be consistent with radiographical progression, in which case the patient should leave the study. Stabilization and shrinkage of a lesion can be consistent with treatment effect, in which case the patient can stay in the study. For patients with equivocal results even on the next restaging scan, the scan can be repeated again at a subsequent protocol-scheduled assessment or sooner, although surgery or use of an advanced imaging modality (in the case of stereotactic radiosurgery), or both, are strongly encouraged. Surgical pathology can be obtained via biopsy or resection.

- a. For lesions treated by stereotactic radiosurgery, additional evidence of tumor progression or treatment effect (radionecrosis) can be acquired with an advanced imaging modality, such as perfusion MRI, magnetic resonance spectroscopy, or ¹⁸FLT or ¹⁸FDG PET. Current recommendations suggest involving a multidisciplinary team to decide on the appropriate next step. Irrespective of the additional testing obtained, if subsequent testing shows that progression has occurred, the date of progression should be recorded as the date of the scan this issue was first raised.

Patients can also have an equivocal finding on a scan (e.g., a small lesion that is not clearly new). Continued treatment is permissible until the next protocol-scheduled assessment. If the subsequent assessment shows that progression has indeed occurred, the date of progression should be recorded as the date of the initial scan where progression was suspected.

- b. In patients receiving immunotherapy-based treatment, an initial increase in the number and size of metastases can be followed by radiographical stabilization or regression. This pattern might be related to the mechanism of action of immunotherapy, including immune infiltrates, and the time to mount an effective immune response. Thus, progressive disease should not be solely defined by the appearance of new lesions but rather as a minimum 20% increase in the sum longest diameter of CNS target and new lesions, as unequivocal progression of existing enhancing non-target CNS lesions, as unequivocal progression of existing non-enhancing (T2/FLAIR) CNS lesions, or as clinical decline related to the tumor. If immune response-related radiographical changes are suspected, we advise to not change treatment until a short interval scan is obtained. If the subsequent assessment confirms that progression has indeed occurred, the date of progression should be recorded as the date of the initial scan where progression was suspected.

Note that the advanced imaging modalities discussed for treatment effect above have not been extensively studied with regards to immunotherapy-based approaches and therefore cannot be recommended to distinguish between tumor progression and immune-related changes at present.

- 6. In the absence of clinical deterioration related to the tumor, an increase in corticosteroid dose alone should not be used as a sole determinant of progression. Patients with stable imaging results and whose corticosteroid dose has increased for reasons other than clinical deterioration related to the tumor do not qualify as having stable disease or progression.

These patients should be observed closely, and if their corticosteroid dose can be reduced back to baseline, they will be considered as having stable disease, but if further clinical deterioration related to the tumor becomes apparent, they will be considered as having progression.

The definition of clinical deterioration is left to the discretion of the treating physician, but it is recommended that patients who have a decrease in score on the Karnofsky performances scale from 100 or 90 to 70 points or less, a decrease of minimum 20 points from 80 or less, or a decrease from any baseline to 50 points or less, for at least 7 days, be considered as having neurological deterioration, unless this functional impairment is attributable to comorbid events, treatment-related toxicity, or changes in corticosteroid dose.

Table 16-3. Response assessment of target and non-target lesions[46]

Target lesions
Complete response
Disappearance of all CNS target lesions sustained for at least 4 weeks; with no new lesions, no use of corticosteroids, and patient is stable or improved clinically.
Partial response
At least a 30% decrease in the sum longest diameter of CNS target lesions, taking as reference the baseline sum longest diameter sustained for at least 4 weeks; no new lesions; stable to decreased corticosteroid dose; stable or improved clinically.
Progressive disease
At least a 20% increase in the sum longest diameter of CNS target lesions, taking as reference the smallest sum on study (this includes the baseline sum if that is the smallest on study). In addition to the relative increase of 20%, at least one lesion must increase by an absolute value of 5 mm or more to be considered progression.
Stable disease
Neither sufficient shrinkage to qualify for partial response nor sufficient increase to qualify for progressive disease, taking as reference the smallest sum longest diameter while on study.
Non-target lesions
Non-target lesions should be assessed qualitatively at each of the time points specified in the protocol.
Complete response
Requires all of the following: disappearance of all enhancing CNS non-target lesions, no new CNS lesions.
Non-complete response or non-progressive disease
Persistence of one or more non-target CNS lesion or lesions.
Progressive disease
Any of the following: unequivocal progression of existing enhancing non-target CNS lesions, new lesion(s) (except while on immunotherapy-based treatment), or unequivocal progression of existing tumor-related non-enhancing (T2/FLAIR) CNS lesions. In the case of immunotherapy-based treatment, new lesions alone may not constitute progressive disease.

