7.4. Tumor Assessment

Standard diagnostic quality MRIs will be ordered for routine follow-up at 3, 6, and 12 months after treatment ends. Please see Appendix 3 for details regarding the Response Assessment in Neuro-Oncology Brain Metastases (RANO-BM) criteria. We plan on adhering to the RANO-BM guidelines except in the following situations:

1. RANO-BM specifies that no more than 5 "target lesions" are followed for the study outcome. Further, it cautions on following lesions > 5 mm but < 10 mm in maximal dimension, but does provide guidelines for this situation. We plan on following all (i.e., potentially > 5) lesions that are treated and > 5 mm in maximal dimension for the study outcome using the RANO-BM suggested criteria for lesions < 10 mm in maximal dimension.
2. We also plan on following treated lesions < 5 mm in size for descriptive assessment as per RANO-BM guidelines. In particular, we agree that it is difficult to reliably reproduce small measurements (i.e., measurements for partial response or slight progression) with such small sizes and the limitation of MRI slice thicknesses. However, as these are treated lesions, we would still like to follow them prospectively.

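### Appendix 3 (16.3.2 item 1) records a small measurable remnant both at its actual size and at 5 mm, and section 7.4 leaves the growth threshold for lesions under 10 mm open, so some regrowth can count as either treated-lesion progression or control.

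*Combined protocol and SAP*

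**What the plan says.** Treated-lesion control is the first secondary outcome (section 3.2). It is a 6-month actuarial rate that takes its definition of progression from Appendix 3.

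- **Recording, section 16.3.2 item 1.** Three sentences govern what is entered. First, "all CNS target lesions should have their actual measurement recorded, even if very small (e.g., 2 mm". Second, "If the lesion disappears, the value should be recorded as 0 mm". Third, after a contrasting conjunction, "if the lesion is sufficiently small (but still present) to be assigned an exact measurement, a default value of 5 mm should be recorded".
- **Progression, Table 16-3.** The relative criterion is "At least a 20% increase in the sum longest diameter of CNS target lesions, taking as reference the smallest sum on study". In addition, "at least one lesion must increase by an absolute value of 5 mm or more to be considered progression". Table 16-4 gives only the 20% rise from nadir. Section 16.3.2 describes both tables as partial summaries.
- **Small lesions, section 16.3.1 item 3a.** Because small measurements are uncertain, "any lesion less than 10 mm in longest diameter should be regarded as unchanged from baseline unless there is a minimum 3 mm change".
- **What this trial adopts, section 7.4.** All treated lesions over 5 mm are followed for the study outcome, "using the RANO-BM suggested criteria for lesions < 10 mm in maximal dimension". Treated lesions under 5 mm are followed descriptively. MRIs are scheduled at 3, 6 and 12 months.

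**The concern.** The first and third sentences of item 1 cannot both be followed for a lesion that is visible and measurable at, say, 2 mm. No size or criterion separates the two cases, so two readers can enter different values and each be following the protocol. The entry matters later because the smallest recorded sum becomes the reference for progression. Section 7.4 sharpens the problem: the smallest lesions that count are just over 5 mm at baseline, so a 5 mm default removes almost all of their shrinkage from the record. The error runs in one direction, since a higher nadir makes regrowth harder to call.

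The second matter is that section 7.4 imports the small-lesion criteria without relating them to Table 16-3. The 3 mm figure is referred to baseline and the 5 mm figure to nadir, and the protocol does not say whether one replaces the other.

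At stake is the outcome that shows whether the boost still controls the treated lesions when the whole-brain dose is lowered. With 20 evaluable patients per cohort (section 10.5), one reclassified patient is 1/20 = 5 percentage points as a crude proportion. The planned analysis is Kaplan-Meier, so the exact shift would differ.

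**Working it through.** The plan gives no figure of its own to reproduce here. The check applies its rules directly. The 2 mm remnant is item 1's own example; the other diameters are illustrative.

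**Rule (Table 16-3):** progression if (current sum − nadir sum) / nadir sum ≥ 20% and at least one lesion has grown by ≥ 5 mm.

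**1. Recording, one lesion, true nadir 2 mm**

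| Regrowth to | Nadir entered as 2 mm | Nadir entered as 5 mm |
|---|---|---|
| 6 mm | +4 mm, +200%: no | +1 mm, +20%: no |
| 7 mm | +5 mm, +250%: **yes** | +2 mm, +40%: no |
| 9 mm | +7 mm, +350%: **yes** | +4 mm, +80%: no |
| 10 mm | +8 mm, +400%: yes | +5 mm, +100%: yes |

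The two entries disagree from 2 + 5 = 7 mm up to just under 5 + 5 = 10 mm.

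This band is Table 16-3 taken alone. If the 3 mm floor against baseline is enforced as well, a lesion under 10 mm at baseline must also exceed its baseline by 3 mm. For a 6 mm baseline the band then shrinks to 9 to <10 mm (6 + 3 = 9). For a baseline of 7 mm or more it closes, because 7 + 3 = 10. The sequence 6, 2, 9 mm flips either way: +3 mm on baseline, +7 mm on the measured nadir, +4 mm on the default nadir.

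**2. Recording, several lesions.** Add two stable lesions of 12 mm (24 mm in total).

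- Regrowth from 2 to 7 mm, entered as 2: the sum goes from 26 to 31, 5/26 = 19.2%, not progression. Entered as 5: 29 to 31, 2/29 = 6.9%, not progression. The recording makes no difference.
- Regrowth from 2 to 8 mm, entered as 2: 26 to 32, 6/26 = 23.1% with +6 mm, progression. Entered as 5: 29 to 32, 3/29 = 10.3%, not progression.

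The sum rule can therefore mask the conflict but does not always do so. Section 3.2 does not say whether progression is judged lesion by lesion or on the sum.

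**3. Threshold, no default involved.** A lone lesion at 6 mm that never shrank, so that baseline and nadir coincide:

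- 6 to 9 mm: +3 mm, 3/6 = +50%. This meets the 20% criterion and the 3 mm floor but not the 5 mm requirement. It is progression if 3 mm replaces 5 mm and control if 3 mm is added to 5 mm. If the lesion is spherical, its volume has grown (9/6)³ = 3.4 times.
- 6 to 11 mm: +5 mm, +83%. Progression on either reading; the volume has grown (11/6)³ = 6.2 times.

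The unresolved band is growth of 3 to <5 mm in a lesion under 10 mm at baseline.

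**The case against.** The strongest reply is that the last sentence of item 1 is a slip. Being small enough to receive an exact measurement makes little sense; too small to receive one does. On that reading a measurable 2 mm lesion is entered as 2 mm and the default covers only remnants that cannot be measured. That is very likely what was meant, and the fix below adopts it. But this is operative endpoint text, it does not say so, and a site has to follow what is written.

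A reader might go further and infer three things that the documents do not support.

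- **That 3 mm and 5 mm are rival progression thresholds.** They are not. The first is a no-change floor against baseline, the second an added condition against nadir for any target lesion, and both can be applied together. What stands is an ambiguity: section 7.4 does not say whether they are meant to be.
- **That Table 16-4 lets a 6 mm lesion progress at 6 × 1.2 = 7.2 mm on the 20% criterion alone.** The table is declared a partial summary, and the 3 mm floor adopted through section 7.4 excludes that case.
- **That many lesions must be under 10 mm because the largest is capped at about 2.1 cm (section 4.1).** An upper limit says nothing about the size distribution, and the documents give none.

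The reach is also limited. To move the 6-month rate through the recording conflict, a lesion must shrink to a tiny remnant by the 3-month scan and regrow into the band by the 6-month scan; section 10.9 also reports a 12-month estimate. Section 3.2 counts recurrent tumor too, so marked regrowth might be captured that way. These points limit the size of the problem without removing it.

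**Conclusion.** The point holds in two parts of unequal strength. The recording instruction contradicts itself as literally written. Under Table 16-3, for a single-lesion patient with a true nadir of 2 mm, that alone decides the outcome for regrowth to 7 to <10 mm, always in the direction of control when 5 mm is entered. The band narrows or closes for lesions under 10 mm at baseline if the baseline floor is also enforced, and can be masked when other lesions contribute to the sum. The threshold question is an unresolved ambiguity, not a contradiction, and concerns growth of 3 to <5 mm in lesions under 10 mm.

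Only treated-lesion control is affected, and no decision rule hangs on it. The primary outcome, the early stopping rule and the interim analysis rest on in-brain distant failure and are untouched. How many patients would be reclassified cannot be estimated from the documents. It should be corrected because the remedy is cheap and the bias runs one way.

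**What to change.** 1. Reword section 16.3.2 item 1 for all target lesions: a measurable lesion is entered at its measured size, an absent one as 0 mm, and the 5 mm default is used only for a lesion that is present but too small to measure. Put the same instruction on the case report form.
2. In section 7.4, state which absolute increase applies to lesions under 10 mm, whether the 3 mm criterion replaces or adds to the 5 mm in Table 16-3, and whether the reference is baseline or nadir. Bring 16.3.1 item 3a and Tables 16-3 and 16-4 into line with that choice.

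Two apparent shortcuts should be avoided. Deleting the default would leave unmeasurable remnants with no value, and section 10.1 rules out imputation; restricting the deletion to lesions under 10 mm at baseline would leave the contradiction in place for larger ones. Writing in a 3 mm rise over nadir would introduce a criterion found nowhere in the documents. It would call the sequence 6, 2, 5 mm progression (+3 mm, +150%) although the lesion is 1 mm below baseline and counts as unchanged under 16.3.1.

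The cost is protocol wording and a form instruction. Reported treated-lesion control may come out slightly lower.

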3.2. Secondary Outcome Measures

1. Treated lesion control, defined as an actuarial 6-month rate of any new, recurrent, or progressing (as defined by RANO criteria, see Appendix 3) tumor within the planning target volume on any post-treatment MRI by 6 months. Follow-up MRIs will be fused with the planning scan for this assessment.
2. Overall survival, defined as an actuarial 6-month rate of patients still alive regardless of disease status at 6 months.
3. Neurocognitive function change, defined as the change from baseline neurocognitive testing scores at a 6-month time point with respect to the HVLT-R.
4. Health-related quality of life change, defined as the change from baseline quality of life assessment at a 6-month time point with respect to the FACT-Br tool.
5. Performance status change, defined as the change from baseline performance status at a 6-month time point with respect to the KPS clinical assessment tool.
6. Incidence of early and late adverse effects as defined by the CTCAE, at any time point during the study follow-up.

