9. CRITERIA FOR REMOVAL FROM THE STUDY

Every subject should be encouraged to remain in the study. Possible reasons for early withdrawal may include, but are not limited to, the following:

1. Withdrawal of consent – Subject decides to withdraw from the study. This decision must be an “independent decision” that is documented in the source documentation.
2. Principal Investigator and/or treating physician discretion – The Principal Investigator and/or treating physician may choose to withdraw a subject from the study if there are safety (or other) concerns.
3. Subject becomes pregnant.
4. Subject non-compliance.
5. Subject lost to follow-up.
6. Subject death.

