10.4.3. Efficacy Population

The efficacy population comprises all subjects who have received at least one dose of radiation, and have been evaluated for the primary endpoint (the 6 month scan). This population will be used for efficacy analysis.

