14.2. Adverse Event (AE) and Serious Adverse Event (SAE) Reporting

Adverse events (AEs) will be recorded from the time of registration through 12 months after treatment (i.e., WBRT-SIB) regardless of whether or not the event(s) are considered related to the study procedure. All AEs considered related to study procedures will be followed until resolution, return to baseline, or deemed clinically insignificant, even if this occurs post-trial. Any death occurring within 30 days after the last study procedure must be reported as an SAE regardless of attribution.

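### Appendix 3 still directs a patient whose lesion keeps growing on a repeat scan to exit the study, which in this trial can only end follow-up that the endpoints need

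*Combined protocol and SAP*

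**What the plan says.** Section 7.4 (Tumor Assessment) makes the appendix operative: "We plan on adhering to the RANO-BM guidelines except in the following situations". The two situations listed are following more than five lesions, including those under 10 mm, and following lesions under 5 mm descriptively. Neither concerns what happens to the patient after progression.

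Appendix 3, section 16.3.2, item 5 deals with enlargement that may be treatment effect rather than tumour. It calls for a repeat scan at the next scheduled assessment or sooner, generally within about 6 weeks. It then says: "Continued tumor growth might be consistent with radiographical progression, in which case the patient should leave the study". If the lesion stabilises or shrinks, the patient may stay.

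Elsewhere the plan expects follow-up to continue:
- Section 3.2 defines overall survival as the actuarial rate of "patients still alive regardless of disease status at 6 months".
- Sections 7.2 to 7.4 schedule HVLT-R, FACT-Br and MRI at 3, 6 and 12 months after treatment, with no exit at progression.
- Section 14.2: "Adverse events (AEs) will be recorded from the time of registration through 12 months after treatment", whether or not related.

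On the analysis side, section 10.4.3 limits the efficacy population to treated subjects evaluated on the 6-month scan, section 10.1 rules out imputation, and section 10.5 speaks of replacing only subjects who die before 6 months without confirmed distant failure.

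**The concern.** The Appendix 3 sentence suits a trial with continuing therapy, where leaving the study mainly means stopping a drug. Here no protocol treatment remains to stop when the first follow-up MRI is read. Taken literally, the instruction does one thing: it ends observation of a patient whose treated lesion is growing.

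Three sets of results are exposed. First, a patient who exits before the 6-month scan falls outside the efficacy population, so the primary proportion is taken over patients with better local control. Second, the 6- and 12-month changes in HVLT-R, FACT-Br and KPS lose patients with intracranial progression. Third, section 10.9 estimates survival and local control by Kaplan-Meier at 6 and 12 months; if survival is censored on leaving because of progression, that censoring is informative.

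The first matters most, because section 10.11 opens the lower-dose cohort on a bare observed rate below 20%.

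**Working it through.** **1. Can exit mean anything other than end of follow-up?** Table 7-1 gives 10 fractions (Cohort A) or 8 (Cohort B), delivered five per week: at most 10/5 = 2 weeks, plus any interruptions. The first scheduled MRI is 3 months after treatment ends. No protocol therapy is left, so the answer is no.

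**2. Can exit come before the 6-month scan?** Take 3 months as day 91 and 6 months as day 183, and assume MRIs follow the ±30-day visit windows in section 8.
- Growth on an on-time 3-month scan, repeated at 6 weeks: 91 + 42 = day 133. The 6-month window opens at 183 − 30 = day 153. Exit before the 6-month scan is possible.
- 3-month scan at the end of its window: 91 + 30 + 42 = day 163, inside the 6-month window.
- Repeat left to the next scheduled assessment: it is the 6-month scan itself. The primary endpoint is then observed, and only later data are at risk.

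**3. The plan's own precision figure.** The 90% half-width at 20% with n = 20 is 1.645 × √(0.2 × 0.8/20) = 14.7%, as section 10.5 states. It allows for sampling error only, not for selective exit.

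**4. Direction.** Section 1.3 cites a phase I integrated-boost trial with 32 assessable patients: 4 with local progression only, 2 distant only, 4 both.
- With local progression: 4/8 = 50% had distant failure.
- Without: 2/24 = 8.3%.
- Overall: 6/32 = 18.8%.

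**5. Illustration from those counts.** Let q be the share of local progressors who leave before the 6-month scan with no distant failure yet seen. No document gives q. The observed rate is (2 + 4(1 − q)) / (24 + 8(1 − q)). Cohort A passes with 3 or fewer failures in 20 (exact binomial).

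| q (assumed) | Observed rate | Chance of passing |
|---|---|---|
| 0 | 6/32 = 18.8% | 47% |
| 0.25 | 5/30 = 16.7% | 57% |
| 0.5 | 4/28 = 14.3% | 68% |
| 0.75 | 3/26 = 11.5% | 81% |
| 1 | 2/24 = 8.3% | 92% |

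The last row requires every local progressor to leave unseen, including the four who had both kinds of failure.

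**6. Sensitivity without the phase I counts.** Let the true rate be 25%, a share L of patients leave, and their distant-failure risk be R times that of the others. The observed rate is 0.25/(1 − L + L × R). All three inputs are assumptions.
- R = 1, any L: 25%; chance of passing 23%. No bias.
- L = 0.1, R = 2: 0.25/1.1 = 22.7%; 30%.
- L = 0.2, R = 2: 0.25/1.2 = 20.8%; 38%.
- L = 0.3, R = 3: 0.25/1.6 = 15.6%; 62%.

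**The case against.** The strongest reply is that this is one hedged sentence in a reproduced guideline, concerned with suspected treatment effect, while the body of the protocol schedules everyone to 12 months and section 9 does not list progression. Much of that is right, and it limits the point in four ways.

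- A reader might infer that every confirmed progression ends participation. The sentence does not say so: it is conditional and follows a repeat scan. The situation is still foreseeable, since Table 7-1 equates the boost to 20 Gy of single-fraction radiosurgery.
- A reader might infer that section 9 removes patients for non-compliance, pregnancy or discretion and so adds to the loss. Its list is permissive ("Possible reasons for early withdrawal may include, but are not limited to, the following"), discretion is optional (the physician "may choose to withdraw a subject from the study if there are safety (or other) concerns"), and it opens with "Every subject should be encouraged to remain in the study". Nothing shows that such withdrawals would favour low distant failure.
- A reader might infer that data will be lost selectively, safety data included. No section says collection stops, and section 14.2 follows related events even after the trial. The risk comes from one instruction and from silence about what follows it.
- A distant lesion seen on the early repeat scan should count, because section 3.1 accepts any post-treatment MRI by 6 months, and the replacement rule implies that confirmed failures are kept. Section 10.4.3 leaves this unclear for a patient with no 6-month scan. The clear exposure is in-field growth followed by exit before distant failure appears.

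The phase I counts are also weak evidence: few patients, no timing, and 22/32 = 69% free of failure beside a stated 75% control rate.

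What remains is the contradiction. Section 7.4 adopts the guideline subject to listed exceptions, and this sentence is not among them.

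**Conclusion.** The concern holds as a conflict between an operative instruction and the endpoints. If followed, the Appendix 3 sentence ends follow-up for some patients with in-field growth, against sections 3.2, 7.2 to 7.4 and 14.2. With an early repeat scan it can remove a patient from the primary denominator; with exit at 6 months it puts the 12-month survival, cognitive, quality-of-life and adverse event data at risk.

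The direction is favourable to the reduced dose if local and distant failure are linked, and neutral if they are not. The size cannot be estimated, because the documents do not say how many patients would meet the condition before 6 months. The fall from 18.8% to 8.3% is an extreme bound from small, undated counts and should not be read as an expected bias. With a cut-off of 3 failures in 20, however, one or two unseen failures could change the Cohort A decision.

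**What to change.** Reconcile Appendix 3, section 16.3.2, item 5 with sections 3.2, 7.2 to 7.4 and 14.2 by adding a third exception to section 7.4. It should state that progression, local or distant, does not end study follow-up, and that scheduled MRI, HVLT-R, FACT-Br, KPS, survival and adverse event assessments continue to 12 months unless the patient withdraws consent to follow-up. Section 9 need only be made consistent with that statement. The change concerns data collection and leaves treatment decisions untouched.

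The cost is one sentence in 7.4, a matching edit in section 9, and the continued attendance of progressing patients at visits already scheduled. It should be in place before it can affect the Cohort A decision, since assessments not made cannot be recovered at analysis.
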